I will conduct the study in accordance with Good Clinical Practice (GCP), the Declaration of Helsinki, and the moral, ethical, and scientific principles that justify medical research. The study will be conducted in accordance with all relevant laws and regulations relating to clinical studies and the protection of patients.

I will ensure that the requirements relating to Institutional Review Board/Independent Ethics Committee (IRB/IEC) review and approval are met. I will provide the Sponsor with any material that is provided to the IRB/IEC for ethical approval.

I agree to maintain adequate and accurate records and to make those records available for audit and inspection in accordance with relevant regulatory requirements.

I agree to promptly report to the IRB/IEC any changes in the research activity and all unanticipated problems involving risks to human patients or others. Additionally, I will not make any changes in the research without IRB/IEC and Sponsor approval, except where necessary to ensure the safety of study patients.

Investigational Site Number

Site or Institution Name

Printed Name of Principal Investigator

Signature of Principal Investigator

Date

PROTOCOL REVISION HISTORY

Protocol Version/Date	Protocol Section (s)	Description of Change
Version 1.0 dated, 13 December 2023	Original protocol.	
Version 1.1 dated, 09 June 2023	Synopsis	Updated study period
	
 • Synopsis • Table 2 • Figure 1 • Protocol Sections: 2.0, 3.0, 4.0, 6.0, 7.0 and 10 	Modified dosing regimen from 7 days to 14 days. Changes made to reflect associated protocol areas such as study design, participant eligibility, study procedures/execution, study treatment and analysis of data.
Version 1.2 dated, 17 July 2023	
 • Protocol Section 6 • Table 4 added 	Modification for clarity and consistency of study treatment dosing and strength of SBI-100 per drop/dose.
	
 • Header, Table 2, Protocol Sections: 7.1, 7.2 and 8.2.2 	Version changed to 1.2. Modified to indicate any failed alcohol or drug test will be repeated.
	
 • Synopsis • Protocol Sections: 6.2.1, 10.2, 	Addition of interim analysis
	
 • Synopsis • Table 2 • Protocol Sections: 2.3, 7.2, 7.5, 8.2.3, 10.4.4, 12.4, 	Addition of biomarker testing
	
 • Synopsis • Table 2 • Protocol Sections: 2.2.1, 3.1; 7.1, 7.3, 7.4, 7.5 	Removal of 8:15 assessments on Day 1, Day 7 and Day 14 and serial assessments of best corrected visual acuity, pupil diameter, slit lamp, vital signs
	
 • Table 2 • Protocol Sections: 7.1, 7.2, 7.6, 8.2.2, 8.2.2.1 (previous, removed), 	Clarification of drug and alcohol screening and removal of End of Study / Early Termination Tetrahydrocannabinol screening
	
 • Table 2 • Protocol Sections: 6.3.3, 6.4.3, 7.1, 7.3, 7.4, 8.1.4, 	Clarification of investigational product diversion and patient education procedures
	
 • Table 2 • Protocol Sections: 7.3, 7.4, 7.5, 8.3.9 	Clarification of Ocular Comfort Patient Reported Outcomes procedure
	Throughout the document	Editorial changes, minor changes for consistency and clarity, updated dates and version change

SYNOPSIS

Name of Sponsor/Company: Skye Bioscience, Inc.	
Name of Investigational Product/Study Treatment: SBI-100 Ophthalmic Emulsion	
Name of Active Ingredient: SBI-100 Delta 9 Tetrahydrocannabinol an amino ester containing valine and hemisuccinate ($\Delta 9$ -THC-Val-HS or THCVHS)	
Protocol Number: SBI-100-201	Country: United States (US)
Title of Study:	A Phase 2, Double-Masked, Randomized, Placebo-Controlled, Dose-Response Study Assessing the Safety and Ocular Hypotensive Efficacy of Two Concentrations of SBI-100 Ophthalmic Emulsion in Patients with Elevated Intraocular Pressure
Study center(s): Multi-center, up to 6 centers	
Studied period (years): Estimated date first patient enrolled: November 2023 Estimated date last patient completed: May 2024	Phase of development: 2
Primary Objective: 
 • To evaluate the diurnal ocular hypotensive efficacy of 2 dose levels of SBI-100 Ophthalmic Emulsion compared to placebo in patients with elevated Intraocular Pressure (IOP) • To evaluate the ocular and systemic safety of SBI-100 Ophthalmic Emulsion in patients with elevated IOP 	
Secondary: 
 • To evaluate the ocular hypotensive efficacy at individual time points of SBI-100 Ophthalmic Emulsion in patients with elevated IOP • To evaluate the application comfort of SBI-100 Ophthalmic Emulsion 	
Exploratory: 
 • Changes in proteomic and immune biomarkers from Baseline 	
Study Design: This is a multi-center, randomized, double-masked, placebo-controlled Phase 2 study to evaluate the ocular hypotensive efficacy, safety, and tolerability of SBI-100 Ophthalmic Emulsion after 14 days of binocular dosing, twice daily (BID). There will be a 35-day screening period, including wash-out (if needed), followed by a visit on Day-1 to confirm eligibility. The first dose will be administered by the staff immediately after the (eligibility) 08:00 IOP measurement on Day 1, with subsequent study assessments up to 8	

hours post-dose. The PM (evening) dose will be self-administered by the patient at home, approximately 12 hours after the AM (morning) dose. The patient will self-administer study treatment on Days 2 through 6 in the AM and PM. On Day 7, the patient will return to have the AM dose administered by site staff immediately after the 08:00 IOP measurement has been taken. Subsequent assessments will be performed in a similar fashion as Day 1 with study assessments up to 8 hours post dose, patient will self-administer the Day 7 PM dose and the AM and PM doses on Days 8 through 13. On Day 14, the patient will return to have the AM dose administered by site and assessments similar to that of Days 1 and 7, the patient may complete the final dose on Day 14 at the site approximately 12 hours after the AM dose and have end of study (EOS) procedures performed. Or the patient may choose to self-administer the Day 14 PM dose at home and return to the site within 2 days for EOS visit.

IOP efficacy will be evaluated by Goldmann applanation tonometry. Safety/tolerability will be evaluated by review of ocular signs and symptoms through Best Corrected Visual Acuity (BCVA), ophthalmic assessments, ocular comfort patient reported outcome (PRO), vital signs, and other standard safety measures.

Number of patients (planned): 54 in total, 18 per treatment group

Diagnosis and main criteria for inclusion: Patients with primary open angle glaucoma (POAG) or ocular hypertension (OHT)

Study Treatment, dosage, and mode of administration: A topical eye drop that is administered binocularly BID with the following treatment groups:

- 0.5% (5 mg/mL) SBI-100 Ophthalmic Emulsion
- 1.0% (10 mg/mL) SBI-100 Ophthalmic Emulsion
- Placebo Ophthalmic Emulsion

Duration of study participation: 52 days in total

Screening:	Up to 35 days, including wash-out from any topical pharmacological IOP-lowering therapies (if required)
Treatment:	2 weeks (14 days)
Follow-up	Up to 2 days after the last dose on Day 14

Inclusion Criteria:

1. At least 18 years of age or greater at time of informed consent.
2. Diagnosis of either primary open angle glaucoma (POAG) or ocular hypertension (OHT) in each eye.
3. Intraocular Pressure (IOP) Criteria:
 - a. If currently on an IOP-lowering therapy, patient is willing to withhold therapy according to study requirements, and in the opinion of the Investigator, can do so without significant risk.
 - b. If treatment naïve, Screening IOP is ≥ 21 and ≤ 36 mmHg in each eye, and in the opinion of the Investigator, is likely to be controlled on a single IOP-lowering therapy.
 - c. 08:00 Hour IOP is between 21 and 36 mmHg in each eye on Day-1 and Day 1.
4. Central corneal thickness between 480 and 620 μm at Screening in each eye.

5. Best correct visual acuity (BCVA) for distance equivalent to 20/100 or better in each eye at Screening and Day 1 (pre-dose).
6. Able to give signed informed consent and follow study instructions.
7. If patient and/or partner has reproductive potential, agrees to use reliable methods of contraception throughout their participation in the study and until at least 30 days after the last dose.
 - a. If female of childbearing potential, has a negative pregnancy test at Screening and Day-1.

Exclusion Criteria:

Either eye:

1. Mean/Median intraocular pressure > 36 mmHg at Screening and/or any time prior to treatment administration.
2. Concurrent treatment for glaucoma requiring more than 2 topical therapies (either as 2 independent monotherapies or as fixed dose combination), oral IOP-lowering therapy and/or in the opinion of the Investigator cannot be controlled on a single IOP therapy.
3. Has planned ocular surgeries/procedures within the duration of the study.
4. In the opinion of the Investigator has clinically significant dry eye disease that requires chronic use of artificial tears, gels and/or ointments.
5. Any abnormality preventing reliable applanation tonometry.
6. History of closed angle forms of glaucoma and/or Shaffer grade < 3 (in 1 or more quadrants); Laser treated narrow anatomic angle is acceptable.
7. Any occurrences of the following prior to Day 1:
 - a. Ocular trauma or surgery within 6 months
 - b. Ocular laser treatments within 3 months
 - c. In the opinion of the Investigator history or evidence of clinically significant ocular inflammation, including but not limited to blepharitis, conjunctivitis, etc.
 - d. History of recurrent ocular herpes (simplex or zoster)
 - e. Previous glaucoma intraocular surgery or glaucoma laser procedure and/or refractive surgery (e.g., radial keratotomy, PRK, SLT, LASIK, etc.) within 6 months
 - f. Ocular medication within 30 days prior, **except for:**
 - i. IOP-lowering therapies (washed-out per study requirements)
 - ii. Lid scrubs
 - iii. Artificial tears, gels and/or ointments to treat dry eye disease that in the opinion of the Investigator is not considered chronic use
8. Clinically significant ocular disease (e.g., corneal edema, uveitis, severe keratoconjunctivitis sicca) which might interfere with the study, including:
 - a. Glaucomatous damage so severe that wash-out of ocular hypotensive medications for at least 52 days is not judged to be safe (i.e., cup/disc ratio > 0.8)
 - b. Persistent allergic conjunctivitis or allergic conjunctivitis that is likely to manifest during the study and confound the results
 - c. Glaucoma: pseudoexfoliation or pigment dispersion component, congenital, developmental, or secondary (e.g., neovascular, uvetic, pigmentary, lens-induced, steroid-induced, trauma-induced, or glaucoma associated with increased episcleral venous pressure) Note: Previous laser peripheral iridotomy is acceptable.

9. Visual field loss, in the opinion of the Investigator, is functionally significant (e.g., split fixation, mean deviation greater than -20 dB or central fixation point equal to 0 dB, or field defect that is visually significant or likely to cause central visual impairment upon progression) or show evidence of fast (> -1.5 dB/year) progressive visual field loss within the 12 months prior to Day 1.
10. Will require contact lenses and cannot refrain from using them at least 7 days prior to Day 1 and throughout the study.

General/Systemic:

11. Clinically significant lab abnormalities at screening and/or systemic disease which might interfere with the study as per the Investigator's discretion.
12. Participation in any investigational study within 30 days of screening.
13. Changes of systemic medication during the study that could have a substantial effect on IOP (5.1.3) within 30 days prior to screening or anticipated during the study.
14. Known hypersensitivity or allergic reaction to cannabinoids, cannabis, sesame seed/oil or any component of the SBI-100 Ophthalmic Emulsion formulation and/or topical anesthetics.
15. Females of childbearing potential (not confirmed as post-menopausal or surgically sterile within the 6 months prior to screening) who are pregnant, nursing, or planning a pregnancy during the study and not using a reliable method of contraception from screening until at least 30 days after the last dose.
16. Males with partners of childbearing potential and do not agree to use a reliable method of contraception during the study and at least 30 days after the last dose.
17. Patients with a history of substance or alcohol abuse, considered chronic tetrahydrocannabinol (THC) users and/or test positive for alcohol or illicit drug use at Screening or Day-1.

Criteria for evaluation:

Efficacy:

- IOP measured by Goldmann applanation

Safety:

- Vital signs, safety labs, and adverse events (AEs) (overall, ocular, and non-ocular)
- Ophthalmic assessments: slit lamp biomicroscopy, dilated fundus exam, BCVA, pupil diameter, visual field and pachymetry
- Ocular comfort

Statistical Considerations:

With a sample size in each group of 18 including 5% attrition (total, n=54), the study will have 80% power to detect a difference of 3.0 mmHg or greater in mean diurnal IOP between each dose of active treatment and its placebo assuming a common standard deviation of 3.0 mmHg in diurnal IOP in each group, $\alpha = 0.05$ (two-sided). All statistical summaries and analyses will be performed using SAS software as detailed in the statistical analysis plan (SAP).

The primary analysis will compare the change from baseline (Day-1) in mean diurnal IOP at Day 14 for each of the SBI-100 treatment groups to the placebo group. Analysis of covariance (ANCOVA) will be used for each comparison, at a two-sided alpha level of 0.05. The model will include adjustment for the Day-1 value. The primary efficacy analysis will be based on

the Intent to Treat (ITT) population. The study eye will be defined as the eye with the highest mean diurnal IOP from the three measures on Day-1 (baseline). (In the case of a tie, the study eye will be the right eye).

For this feasibility study, the primary analysis will be based on observed data only, not imputing missing data. If the study eye is missing data for any time point on Day 14, the mean diurnal IOP will not be calculated for the primary analysis to avoid using a biased estimate. Thus, the while-on-treatment strategy for handling intercurrent events of early discontinuation will be employed.

Sensitivity analysis will be described *a priori* in the SAP and will include analyses on the Per Protocol population should there be a significant number of major protocol deviations. In the case of >5% of patients with missing data for any time point, primary analysis will be repeated on the ITT population with imputed missing data (at the visit and time point level) following other intercurrent event strategies. Other methods for defining the study eye and analyzing both eyes in a random effects model may also be considered.

Secondary efficacy endpoints will be analyzed using MMRM. Safety endpoints will be summarized descriptively.

There will be one interim analysis when at least 50% treated patients have diurnal IOP measurement at 14 days post-dosing to assess the conditional study power.

TABLE OF CONTENTS

TITLE PAGE	1
SIGNATURE PAGE	2
INVESTIGATOR'S AGREEMENT	3
PROTOCOL REVISION HISTORY	4
SYNOPSIS	5
1. INTRODUCTION	18
1.1. Background.....	18
1.1.1. Disease 18	
1.2. SBI-100.....	19
1.3. Summary of Nonclinical Studies.....	19
1.3.1. Pharmacology 19	
1.3.2. Pharmacokinetics 19	
1.3.3. Toxicology 19	
1.4. Clinical Studies.....	20
1.5. Summary of Potential Risks and Benefits	20
1.6. COVID-19 Risk Assessment	21
2. STUDY OBJECTIVES AND PURPOSE	22
2.1. Primary Objectives and Endpoints	22
2.1.1. Primary Objectives 22	
2.1.2. Efficacy Endpoints 22	
2.1.3. Safety Endpoints 22	
2.2. Secondary Objectives	22
2.2.1. Efficacy Endpoints 22	
2.2.2. Safety Endpoints 22	
2.3. Exploratory Objectives	23
3. INVESTIGATIONAL PLAN.....	24
3.1. Overall Study Design.....	24
3.1.1. Number of Patients 25	
3.2. Measures to Minimize Bias:	25
3.2.1. Randomization/Masking 25	
3.2.2. Determination of Study Eye 25	
3.3. Study Design Rationale	25
3.3.1. Design Rationale 25	
3.3.2. Criteria for Dosing 25	
3.4. End of Study Definition.....	26
3.5. Criteria for Study Termination	26

4.	SELECTION AND WITHDRAWAL OF PATIENTS	30
4.1.	Inclusion Criteria	30
4.2.	Exclusion Criteria	30
4.3.	Withdrawal Criteria	32
4.3.1.	Screen Failures 32	
4.3.2.	Early Termination of Patients 32	
4.3.3.	Procedures for Early Termination33	
5.	STUDY REQUIREMENTS	34
5.1.	Prior and Concomitant Medications/Procedures	34
5.1.1.	Permitted Medications/Procedures 34	
5.1.2.	Prohibited Medications/Procedures 34	
5.1.3.	Wash-out of IOP-Lowering Therapies 35	
5.1.4.	Rescue Medication/Therapy 35	
5.2.	Study Restrictions.....	35
5.2.1.	Contact Lens Use 35	
5.2.2.	Prevention of Pregnancy 36	

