10. STATISTICS

10.1. Determination of Sample Size

From prior studies, the expected standard deviation (SD) of diurnal IOP in each treatment group ranges from 2.0 to 3.0 mmHg, with an average of 2.7 mmHg. The following estimates rely on a conservative SD of 3.0 mmHg for all visits and time points.

Analyses will be performed using a 2-sided alpha level of 0.05 for each test. For this feasibility study, no adjustments will be made for multiple comparisons across the multiple treatment groups versus the control group, or across tests for multiple visits and time points.

Sample sizes for both 80% and 90% power, and assuming a pooled SD of 3.0, are shown. The table below summarizes the sample size requirements for various expected differences in mean diurnal IOP between the active treatments and placebo. Sample sizes are shown prior to considering dropouts or non-compliance for the various endpoints and assumptions.

Table 5: Sample Size Requirements

Endpoint: Superiority of treatment over placebo for change from baseline (Day-1) at Day 14; SD = 3.0		
	Power	
	80%	90%
Difference (SBI-100 – Placebo) = 3.0	17	23
Difference (SBI-100 – Placebo) = 3.5	13	17
Difference (SBI-100 – Placebo) = 4.0	10	13

For this feasibility study, a difference of 3.0 mmHg in mean diurnal IOP between treatment and placebo is assumed with 80% study power.

Accounting for up to 5% dropout over a short-term study, an additional ~5% will need to be enrolled in each treatment group. For an expected difference of 3.0 mmHg at 80% power, $17/95\% = 18$ patients per treatment group will need to be enrolled, for a total of 54 patients in this 3-treatment group study.

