10.4.2. Primary Endpoint

The primary analysis will compare the change from baseline (Day-1) in mean diurnal IOP at Day 14 for each of the SBI-100 treatment groups to the placebo group. ANCOVA will be used for each comparison at a two-sided alpha level of 0.05 without any adjustment as described in [10.4.6](#). The model will include adjustment for the baseline value. The primary efficacy analysis will be based on the ITT population.

The null hypothesis for the primary endpoint is as follows:

The change from baseline (Day-1) in mean diurnal IOP of each dose level of SBI-100 Ophthalmic Emulsion will not be different from that of its placebo after 14 days of BID dosing.

For this feasibility study, the primary analysis will be based on observed data only, not imputing missing data. If the study eye is missing data on Day 14, the mean diurnal IOP will not be calculated for the primary analysis to avoid using a biased estimate. Thus, the while-on-treatment strategy for handling intercurrent events of early discontinuation will be employed.

The actual mean diurnal IOP values at each visit will be analyzed with MMRM.

Sensitivity analysis will be described *a priori* in the SAP and will include analyses on the Per Protocol population should there be a significant number of major protocol deviations. In the case of >5% of patients with missing data for any time point, the primary analyses will be repeated on the ITT population with imputed missing data (at the visit and time point level) following other intercurrent event strategies. Other methods for defining the study eye and analyzing both eyes in a random effects model may also be considered.

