10.4.3. Secondary Endpoints

Other secondary endpoints will be analyzed using the method described in [10.4.1](#). Full details of the analyses will be provided in the SAP.

Changes from time-specific baseline in IOP measure and differences in change from 8:00 IOP measure at 10:00 and 16:00 between Pre-dose (Day -1) and Post-dose visits (Day 1, Day 7, and Day 14) will be analyzed using MMRM. Medication comfort responses will be analyzed on a

continuous scale and categorically in a similar fashion. Full details of the analyses will be provided in the SAP.

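### One missed Day 14 reading of three removes the patient from the primary ANCOVA, and the 5% allowance is worded for dropout only; a Day 14 repeated-measures model would keep these patients.

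*Protocol*

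**What the plan says.** The primary endpoint is the change from Day -1 to Day 14 in mean diurnal IOP in the study eye, from readings at 08:00, 10:00 and 16:00. It is analysed by ANCOVA with the baseline value in the model, on observed data without imputation.

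- Synopsis, Statistical Considerations: "If the study eye is missing data for any time point on Day 14, the mean diurnal IOP will not be calculated".
- Section 10.4.2: "If the study eye is missing data on Day 14, the mean diurnal IOP will not be calculated for the primary analysis". The qualifier about any time point is absent.
- Both places give avoidance of bias as the reason and label the result a while-on-treatment strategy for early discontinuation.
- Both places also plan a repeat of the primary analysis on the ITT population, with values imputed by visit and time point, if more than 5% of patients have missing data for any time point.
- Section 10.1, on the allowance: "Accounting for up to 5% dropout over a short-term study, an additional ~5% will need to be enrolled in each treatment group". The synopsis calls the same 5% attrition.
- Section 10.1, on the planning SD: "The following estimates rely on a conservative SD of 3.0 mmHg for all visits and time points". The SD expected from prior studies "ranges from 2.0 to 3.0 mmHg, with an average of 2.7 mmHg".
- Section 10.4.3 already assigns a mixed model for repeated measures (MMRM) to the IOP outcomes by time point, beginning with "Changes from time-specific baseline in IOP measure".

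**The concern.** A raw average of two of the three readings would mix the treatment effect with the diurnal pattern, so the stated reason is a fair argument against that average. It does not follow that the patient has to be excluded. With the baseline-adjusted ANCOVA, leaving out incomplete days is unbiased only if, given treatment and baseline, completeness of the Day 14 curve is unrelated to the Day 14 IOP. The readings that were taken carry most of the missing information and go unused in the primary comparison.

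Two things are at stake. One is the number of evaluable patients: the reserve is one patient per arm and is worded as dropout, with nothing set aside for a patient who attends Day 14 but misses one reading. The other is the definition of the primary analysis set. The section 10.4.2 wording could be taken to exclude only patients with no Day 14 data, so the two places should say the same thing.

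**Working it through.** **Inputs from section 10.1.** Alpha: "Analyses will be performed using a 2-sided alpha level of 0.05 for each test". Effect and target: "a difference of 3.0 mmHg in mean diurnal IOP between treatment and placebo is assumed with 80% study power". Planning SD 3.0, average SD 2.7, 17 evaluable and 18 enrolled per arm.

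**Inputs assumed here.** The protocol gives no rate of missed readings and no within-day correlation. I use a miss rate p of 1%, 2%, 3% or 5% per reading, independent across the three readings, on top of the full 5% dropout, and a correlation ρ of 0.6 to 0.9.

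**Step 1: reproduce the plan.** Two-sample t-test, noncentral t with 2n − 2 degrees of freedom and noncentrality 3.0 / (SD × √(2/n)). At SD 3.0, 17 per arm gives 80.7% and 16 gives 78.1%, so 17 is the smallest n reaching 80%. The other five cells of Table 5 (23, 13, 17, 10, 13) also reproduce. Then 17 / 0.95 = 17.9, rounded up to 18, and 3 × 18 = 54.

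**Step 2: power by complete Day 14 curves per arm.**

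| Complete per arm | Lost of 18 | SD 3.0 | SD 2.7 |
|---|---|---|---|
| 18 | 0 | 83.0% | 89.9% |
| 17 | 1 | 80.7% | 88.1% |
| 16 | 2 | 78.1% | 86.0% |
| 15 | 3 | 75.3% | 83.6% |
| 14 | 4 | 72.1% | 80.8% |
| 13 | 5 | 68.7% | 77.6% |

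**Step 3: dropout plus missed readings under the synopsis rule.** Evaluable n per arm = 18 × 0.95 × (1 − p)³.

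| p per reading (assumed) | Total loss | Evaluable per arm | SD 3.0 | SD 2.7 |
|---|---|---|---|---|
| 0% | 5.0% | 17.1 | 81.0% | – |
| 1% | 7.8% | 16.6 | 79.7% | 87.3% |
| 2% | 10.6% | 16.1 | 78.4% | 86.2% |
| 3% | 13.3% | 15.6 | 77.1% | 85.1% |
| 5% | 18.6% | 14.7 | 74.3% | 82.7% |

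If the misses cluster in the same patients, the loss is smaller than this.

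**Step 4: what a patient with two of three readings contributes.** Under compound symmetry, the share of information on the three-reading mean is 2(1 + 2ρ) / (3(1 + ρ)).

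- ρ = 0.6: 2 × 2.2 / (3 × 1.6) = 4.4 / 4.8 = 0.92.
- ρ = 0.9: 2 × 2.8 / (3 × 1.9) = 5.6 / 5.7 = 0.98.

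With one reading the share is (1 + 2ρ) / 3, that is 0.73 to 0.93. Weighting patients by these shares, effective n per arm for p of 1% to 5% is 16.9 to 17.1, and power at SD 3.0 is 80.4% to 80.9%.

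**Step 5: agreement with the planned analysis.** When every patient has all three readings and each time point has the same regressors (treatment and baseline mean), the generalised least squares estimates equal ordinary least squares at each time point. Their equal-weight average is then the ANCOVA estimate for the mean. The two analyses differ only when readings are missing.

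**The case against.** The strongest case for the plan has five parts.

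1. *The stated power is correct.* This stands. A reader might infer from the exclusion rule that the trial does not have its 80% power. The document does not support that: the figure reproduces, it holds if dropouts and incomplete days together stay within 5%, and every loss in step 3 comes from an assumed rate.
2. *The planning SD is conservative.* This also stands. At SD 2.7 all four scenarios keep at least 82.7%. But 3.0 is the SD on which the stated power rests, and there the reserve is one patient per arm.
3. *Missing data are already handled.* In part. All four scenarios with missed readings lose more than 5% in total, so, counting dropouts, the imputed repeat would be triggered in each. Partial-day readings can also enter the secondary time-point MMRM. Neither changes the primary result.
4. *Loss need not be selective.* This stands. It is tempting to argue that patients with high morning readings are rescued or sent home and so lose the 16:00 reading. Section 5.1.4 does not say so: its guidance mentions a re-check within a day, and rescued patients remain in follow-up. Selective loss is possible, but it is not described.
5. *The two wordings do not conflict.* Largely so. Section 10.4.2 reads most naturally as a shortened form of the synopsis, with the same reason attached. It is an alignment point.

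Sections 10.1 and 10.4.6 also describe the trial as a feasibility study with a hypothesis-generating primary analysis, which limits the weight of a shortfall of one or two points. It is no reason to leave collected primary-endpoint data unused when a planned method can use them.

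**Conclusion.** The point holds as a low-cost improvement to the primary analysis, not as an error in the power calculation. The synopsis rule excludes a patient for one missed Day 14 reading, relies on restrictive assumptions about why it was missed, and draws on a reserve of one patient per arm that is worded as dropout.

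At SD 3.0, power falls below 80% once more than one patient per arm lacks a complete Day 14 curve, at about 2.6 points for the first such extra loss (80.7% to 78.1%). At SD 2.7 up to four of 18 per arm can be lost with power still at 80.8%. How far power would actually fall is unknown, because it depends on a miss rate that the protocol does not give. The power figures use the unadjusted t-test that reproduces Table 5 and credit no gain from the baseline covariate.

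**What to change.** In the synopsis and section 10.4.2, with identical wording:

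- Estimate the primary contrast from a repeated-measures model of the 08:00, 10:00 and 16:00 study-eye readings on Day 14, with treatment by time, baseline mean by time and an unstructured covariance.
- Report, for each dose against placebo, the equal-weight average of the three treatment differences.
- Include every randomised patient with at least one Day 14 reading, and handle readings after rescue or treatment stop according to the intercurrent-event strategy that the protocol names.
- Keep the complete-day ANCOVA and the imputed repeat as sensitivity analyses.

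The cost is a change of wording in two places, the matching SAP text and one model statement. No patients, visits or measurements are added. The downside is that patients with a partial day enter under a missing-at-random assumption, which should be stated.
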